1.1. Preliminary studies

Randomized controlled, comparative trial of social skills groups for youth with ASD

The proposed trial builds upon an NIH-funded, randomized comparative trial of a social cognitive skills therapy group¹⁶. The study was designed to address several methodological limitations in SST research including questions regarding specificity of treatment effects and treatment durability¹³; and investigate behavioral and neural mechanisms underlying treatment response¹⁹. The NIMH trial built upon open-label pilot data collected in outpatient therapy clinics and imaging data from the co-PI, [name], indicating effortful, top-down processing strategies, such as those used in CBI, normalized mentalizing networks in youth with ASD⁴⁹. Method: The study enrolled a well-characterized, ethnically diverse sample of verbal, 8-11 year old youth with ASD (n=69) into an RCT of NETT compared to a facilitated play group. NETT is a 12-session CBI with concurrent child and parent training groups. The facilitated play group served as a control for time, therapist training, peer exposure, and parent engagement.

[figure not shown]

Figure 2: Improvements in social behavior from Seaver-NETT

Measurement: Outcomes collected at baseline, endpoint, and 3-month follow-up included 1) social cognition, neuropsychological assessments conducted by blinded raters, 2) social behavior composite, parent/caregiver ratings on standardized assessments and 3) neural outcomes, on fMRI tasks of eye gaze and interpretation of irony. In addition, experimental measures of peer interactions in familiar and unfamiliar settings were also piloted.

Data analysis. Principal components analysis was conducted on assessments to yield composite scores for social cognition and social behavior. Mixed model analyses were conducted on individuals with two or more time-points (i.e., completers). Variables examined for moderation effects were: VIQ, autism symptoms, comorbid mental health conditions including hyperactivity and anxiety (i.e., BASC-3).

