5.2. Study Procedures

Screening Visit(s)

Participants and their parent(s)/legal guardians will come in to sign informed consent and meet with a study clinician to establish eligibility. The following measures will be obtained: a diagnostic assessment, including the ADOS-2 (if required) and DSM-V interview, the ADI-R (if required), a cognitive assessment (WASI-II, KBIT, or WISC-V, if required), the ABC, the CGI-S (Global and Social), the AE rating form, height, weight, vital signs, temperature, a physical examination, review of medical and psychiatric health and concomitant therapies, and a pregnancy test (if applicable). The ADOS-2 (if required) will be video recorded. The screening visit is anticipated to take approximately 4-6 hours to complete. The visit can be split into two visits if this is better for the participant and may be combined with the baseline visit to facilitate scheduling and compliance with visit windows. If required, the following measures can be completed virtually: consenting, DSM-V interview, ADI-R, CARS2, the ABC, the CGI-S (Global and Social), the AE rating form, review of medical and psychiatric health and concomitant therapies.

ECG and safety lab assessments will be completed no more than 30 days before the first dose of medication is administered.

In addition, a physical exam will be conducted, and height, weight, temperature, and vital signs will be obtained. At the baseline visit, the participant will also be randomized to receive either ION-ASD or control (social play), and the research pharmacy will be notified by research staff to dispense a two week supply of study drug to families assigned to ION-ASD. Blood work will be collected prior to participants taking their first dose of study medication. The randomization form will be developed prior to screening/recruitment for each cycle and present randomization schema for 10-12 participants each time. Coordinators will open the Randomization form after the completion of baseline assessments.

Screening and baseline procedures may be combined to accommodate participant schedules.

Baseline Visit(s)

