Caregiver reports on the ABC, PDDBI-SV, Griffith Empathy Scale, Children's Communication Checklist, CASI-5, Caregiver Strain, Vineland 3, SRS-2, RBS-R, and AIM will be collected at midpoint along with CGI-I ratings (blinded). Ratings may be conducted +/- 7 days from week 6 group depending on family schedules.

Week 12 (Endpoint)

The end of treatment visits occurs at Week 12 (to take place within \pm 7 days from the target date). At these visits, blood work, vital signs, temperature, height, weight, and an ECG will be completed. In addition, participants will undergo a series of assessments, which are anticipated to take approximately 4-6 hours to complete. The visit can be split into as many as three visits if this is better for the participant. The following measures will be completed: the CGI-I (Global and Social), the AE rating form, the Bates & Reilly Conversational Task, the CY-BOCS, Let's Face It, the RMET, the CASI-5, the RBS-R, the SRS, the ABC, the BFRT, the BASC-3, the PDDBI-SV, the Griffith Empathy Scale, the CCC, the Caregiver Strain, the DANVA2, the TAT, , and the GEMEP emotion recognition test, and sensor-based social-communication monitoring tests.

Week 16 & Week 24 (Maintenance visits 1 & 2)

There will be an additional follow-up appointment 12 weeks (\pm 7 days) after the participant stops taking the study drug. This visit is primarily to examine safety of OXT discontinuation, and look for possible maintenance of any favorable effects of ION-, and longer term safety. The assessments completed during this visit are identical to the Week 12/end of treatment visit.

Termination Visit: A participant may voluntarily withdraw from the study at any time. The PI has the right to discontinue a subject from this study or withdraws a participant from the study at any time. Every effort will be made to obtain information on subjects who withdraw. Participants who discontinue study drug prematurely will be asked to return to the clinic and complete all end of study safety lab work (week 12 blood work).

Participants will also be asked to complete all endpoint study procedures on their final visit before withdrawal to allow for true intent to treat analysis.

Missed Visits and Visit Windows

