8.8. Statistical analysis

Specific Aim 1 & Exploratory Aim 1: Safety and tolerability will be analyzed by analyzing for group differences on total scores and domains of the AE form and satisfaction surveys respectively. Efficacy analysis will be follow analytic procedures used to derive social behavior and social cognition composites for the Seaver-NETT RCT¹⁶. First, a principal components analysis with varimax (orthogonal) rotation will be conducted on subscales of the primary social behavior measures - Griffith Empathy Scale and CCC-2; and raw total scores on primary social cognition outcomes – RMET and DANVA2. The PCA is used to develop composite scores in a field with no viable outcomes for higher-order core social impairments as well as to minimize floor and ceiling artifacts, effects of variability in response, and other sources of measurement error. Variables with high factor loadings for subscales will be entered into composite score development for the social cognition and social behavior composites. Missing, invalid, and/or incomplete data (i.e. more than 30% items missing when not pre-defined by scale) will be excluded from the factor analysis.

A linear mixed model analysis will be conducted on all participants with at least two of four available time points (Wk 0, Wk 12, 1-mon, 3-mo). Composite scores of co-primary outcomes social behavior and social cognition will be used as the response variable; treatment condition, time, and condition * time interactions will be covariates. Verbal IQ will also be entered into the model in exploratory moderator analyses. We will estimate effect sizes (Cohen's d) and confidence intervals (95%) acknowledging the likelihood that analyses may not permit definitive conclusions given the likely size of the confidence intervals.

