Prior to the PCAs, missing, invalid, and/or incomplete data will be removed. For SBI, observations missing one or more items on either CCC-2 subscale and/or greater than 30% of GEM items will be removed. For SC, observations with less than 50% of the responses (due to administrative error) on the RMET and/or DANVA2 will be removed. Provided these measures have high and near comparable component loadings on a single factor for each domain, thus confirming previous findings, they will be combined for separate composite scores for social behavior impairment (SBI) and social cognition (SC). To create the SBI composite score, total score on the GEM is reversed so that the higher scores reflect greater impairment as on the CCC-2. To create the SC composite score, percent correct was calculated for the RMET and DANVA-2 since they differ in total number of items and to adjust the denominator when all items were not presented due to administrative error. Subsequently, for each measure, scores will be standardized using the sample mean (and standard deviation) at baseline to account for change from baseline analyses, different and wide ranges of scores, and to ensure that composite scores across domains can be easily compared on the same scale (i.e., z-score). Following outlier detection (see below), standardized scores for each domain (SBI, SC) will then be averaged together to generate final composite scores at each time point. As such, a change in composite score reflects a change from baseline.

Outlier Detection. Individual scores from measures that are either influential points or outlier values (i.e., based on Cook's distance $> .5$ and/or Bonferroni-corrected outlier based on r-student residuals, respectively) and plausibly invalid (e.g., due to clinical reasons or administrative errors) will be removed. Composite scores will then be re-standardized and remaining extreme outliers (>3 SD above the mean for a specific timepoint) will be removed if they change the model significantly ($>10\%$ change in estimated values).

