Data Analysis. Primary: Composite scores of both primary outcomes (i.e., SBI and SC) will be used as the response (i.e., outcome) variable in a series of mixed-effects linear regression models using the *lmer* package in *R Studio* to assess the effect of treatment condition (ION-ASD vs. Facilitated Play), time (e.g., change from baseline after 12 weeks), and condition X time interaction. Across all models, the individual participant will be included as the random effect. Age, verbal IQ, ADHD and generalized anxiety (from the Child & Adolescent Symptom Inventory-5 [CASI-5] T-scores) will be entered into the model to be examined as potential covariates and/or moderators to outcomes as in prior work. We will estimate effect sizes (standardized Betas) and confidence intervals (95%) acknowledging the likelihood that analyses may not permit definitive conclusions given the likely size of the confidence intervals. Finally, if the statistical assumptions of the model are not met (e.g., homoscedasticity, normality, linear relationships), generalized linear models with appropriate link functions or potential transformations of predictor variables will be assessed.

Secondary Outcomes. The linear mixed-effects models will also be used on secondary outcome measures: SRS T-score, mean Caregiver Strain Global rating scale. Responder (i.e., Clinical Global Inventory-Improvement [CGI-I]) analysis will be conducted using either a Chi-squared or Fisher's exact test (when observations are small such that $>20\%$ of cells have *expected* count <5) on the number of responders (i.e., CGI-I scores of 1-2) versus non-responders (i.e., CGI-I scores of 5-7) by group.

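### No single primary analysis set is defined, and the protocol's two-of-four-visits rule drops randomised children on the basis of what happens after randomisation

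*Protocol*

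**What the plan says.** - **Protocol 8.8 (Statistical analysis):** "A linear mixed model analysis will be conducted on all participants with at least two of four available time points", the four being "Wk 0, Wk 12, 1-mon, 3-mo". The composite is the response; condition, time and their interaction are the model terms.
- **Protocol 1.1 (Preliminary studies):** the same rule is described for the earlier NETT trial, with the protocol's own gloss: "Mixed model analyses were conducted on individuals with two or more time-points (i.e., completers".
- **Protocol 5.2 (Termination Visit):** withdrawing children are asked to complete the endpoint procedures at their last visit "to allow for true intent to treat analysis". It does not say which time point those assessments belong to.
- **Protocol 5.2 (Screening Visit(s)):** "Coordinators will open the Randomization form after the completion of baseline assessments". A randomised child should therefore already hold the first of the four time points.
- **Protocol 5.2 (Week 6):** "Caregiver reports on the ABC, PDDBI-SV, Griffith Empathy Scale" and the Children's Communication Checklist are among the midpoint measures. Both social behaviour instruments are thus collected at a visit that 8.8 does not count.
- **SAP:** "Across all models, the individual participant will be included as the random effect". No analysis set is named and no minimum number of visits is given. Exclusions concern observations, not children: "Prior to the PCAs, missing, invalid, and/or incomplete data will be removed", followed by outlier rules.

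**The concern.** The rule in 8.8 selects on a post-randomisation event. Because baseline comes before allocation, the children it removes are mainly those with no counted visit afterwards. They can include a child with social behaviour scores at baseline and Week 6.

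A likelihood-based mixed model does not need the rule, since a child with only a baseline score still informs the baseline mean of that arm. Here this matters because baseline is part of the response and each arm has its own baseline mean. If the lost children were more severe at baseline, deleting them lowers the retained baseline mean. The retained children then regress upwards, and this enters the arm's estimated change.

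Differential loss is plausible, though not shown. Families and treating clinicians know the allocation, and only one arm has nasal dosing four times a week. With no single set defined, the choice of population could also be made after the data are seen. The baseline sample on which the SAP standardises both composites is likewise left undefined.

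**Working it through.** **The plan's own figures.** Section 8.9 gives 25 per group, 5% attrition, a difference of 0.40, an SD of differences of 0.670 and 80% power. The 80% reproduces as a one-sample or paired t calculation (79.98% at n = 24). The same inputs in a two-sample t comparison with 25 per arm give 54.3%. That is a separate matter; only the SD and the attrition rate are used here.

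- Standard error of a two-arm difference, 0.670 × √(2/n): 0.190 at 25 per arm and 0.160 at 35 per arm (the 70 children of Phase 2).
- At 5% attrition the rule removes at most about 0.05 × 50 = 2.5 or 0.05 × 70 = 3.5 children.

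**Formula.** Take no true effect, equal variances, baseline-to-Week 12 correlation ρ, and a fraction r lost from one arm before any later visit, with mean baseline m (in SD units) among those lost.

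- The retained baseline mean is −s, where s = r·m/(1 − r).
- The retained Week 12 mean is −ρs.
- Two-visit rule: mean change = −ρs + s = (1 − ρ)s. This is the bias.
- All children kept: the likelihood estimate of the Week 12 mean is −ρs + ρ(0 − (−s)) = 0, so there is no bias when loss depends only on the observed baseline.

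**Numbers.** Assumed, not in the documents: log-odds of loss rise by 1 per baseline SD (2.7-fold odds), ρ is 0.5 to 0.7, and loss occurs in one arm only. The mean m comes from numerical integration of this logistic loss over a standard normal baseline.

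| Loss r | m | s = r·m/(1 − r) | Bias at ρ = 0.7 | Bias at ρ = 0.5 |
|---|---|---|---|---|
| 5% | 0.895 | 0.047 | 0.014 | 0.024 |
| 10% | 0.817 | 0.091 | 0.027 | 0.045 |
| 15% | 0.751 | 0.133 | 0.040 | 0.066 |

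Simulation of the same scenarios gives 0.01–0.03, 0.03–0.05 and 0.04–0.06, which agrees to within about 0.01. As an extreme, if exactly the most severe 10% leave, s = 0.1755/0.9 = 0.195 and the bias is 0.06 to 0.10.

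**Units.** These are baseline SDs, whereas 8.9 works with an SD of 0.670. If 0.670 is the SD of change, the baseline SD is 0.670/√(2(1 − ρ)), or 0.67 at ρ = 0.5 and 0.865 at ρ = 0.7. The 5% row then becomes 0.024 × 0.67 = 0.016 and 0.014 × 0.865 = 0.012, against a standard error of 0.16 to 0.19.

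**Loss in both arms.** Large-sample random-intercept calculations with four visits and a true Week 12 effect of −0.40 SD (negative favours ION-ASD). The first percentage is ION-ASD. Loss is sharper than in the table above: the children with the highest noisy severity leave.

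| Loss mechanism (assumed) | ION-ASD vs control loss | All randomised, ρ = 0.5 / 0.7 | Two-visit rule, ρ = 0.5 / 0.7 |
|---|---|---|---|
| Unrelated to scores | 20% vs 5% | −0.40 / −0.40 | −0.40 / −0.40 |
| Baseline-related, equal | 20% vs 20% | −0.40 / −0.40 | −0.40 / −0.40 |
| Baseline-related | 10% vs 5% | −0.40 / −0.40 | −0.36 / −0.38 |
| Baseline-related | 20% vs 5% | −0.40 / −0.40 | −0.29 / −0.34 |
| Unseen Week 12 score | 20% vs 5% | −0.56 / −0.51 | −0.51 / −0.46 |

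In the last row both sets are biased, and keeping everyone is the worse of the two.

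**The case against.** The strongest reply is that the conflict is thin and the bias hypothetical. Much of this stands.

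- A reader might infer that three places prescribe three different populations. The documents do not support that. Section 5.2 states a purpose for collecting data and defines no population. The SAP is silent on a minimum number of visits; it does not contradict 8.8. What remains is that 8.8 states a restriction the SAP does not repeat, and nothing says which governs.
- Section 5.2 may soften the rule. If a withdrawing child's last assessment counts as Week 12, that child has two time points and stays in. The mapping is not stated, so this mitigation is possible but not assured. The rule also keeps any child with baseline plus one later counted visit, which is broader than the word completers suggests.
- At the planned 5% attrition the shift is about a tenth of a standard error or less on the unit conversion above. The larger figures need more loss than planned and a marked imbalance between arms, and nothing in the documents predicts either.
- This is a pilot that concedes limited precision, and the rule is pre-specified to match the earlier trial. That justifies keeping the two-visit analysis, but not as the primary one when the stated purpose is intent-to-treat.

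A reader might also infer that the rule manufactures a benefit for ION-ASD. If the arm with the dosing burden loses its more severe children, the rule works against ION-ASD. Nor does keeping everyone cure missing data in general, as the last row of the second table shows.

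**Conclusion.** The point holds in a limited form. The plan does not define one primary analysis set, and the only rule it states excludes randomised children because of post-randomisation events. The resulting bias is conditional: it needs loss that differs by arm and is related to baseline severity, and it disappears if loss is unrelated to scores or is the same in both arms.

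With loss in one arm only, 2.7-fold odds per SD and a correlation of 0.5 to 0.7, all assumed, the shift runs from 0.014–0.024 baseline SD at 5% loss to 0.040–0.066 at 15%. At the attrition the protocol plans for, it would not change the reading of the trial. The case for changing the text is that the better rule costs almost nothing and closes an open choice of population; it does not rest on a large expected bias. Expressing these shifts directly as a share of the planned 0.40 would be unsafe, because that figure is not shown to be in baseline SD units.

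**What to change.** In protocol 8.8 and in the SAP:

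1. Define the primary set as all randomised children, analysed as randomised, with a composite score at any visit. Keep baseline-only children, and apply the definition separately to SBI and SC.
2. State the time point to which a withdrawing child's final-visit assessment is assigned.
3. Keep the set with two or more visits as a sensitivity analysis.
4. Add a missing-not-at-random sensitivity analysis, since step 1 does not protect against loss that depends on unseen outcomes.

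The change of set takes about one sentence per document and no new data; the mapping rule and the added sensitivity analysis need a few lines more. The primary result becomes slightly less directly comparable with the earlier trial, which the two-visit sensitivity analysis covers.

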4.2. Efficacy Assessments

Efficacy assessments will be evaluated through questionnaires, direct assessments of social cognition, and questionnaires surveying quality of life, social functioning, anxiety, & repetitive behaviors.

Primary Outcome Measures. This study has two primary outcomes reflective of the dual treatment targets to underlie social learning in school-age children: social cognition and social behavior. Each outcome will be measured by a composite score developed through a factor analysis of measures in each domain in the Seaver-NET RCT¹⁶.

1. Social Behavior Composite. (Baseline, Week 12, Week 16, Week 20)
 - a. *Children's Communication Checklist (CCC)*⁵⁵. The CCC⁵⁵ is a 70-item caregiver rating scale which includes language scales (e.g. speech, syntax) and pragmatic scales (e.g. scripted language, nonverbal communication, social relations).
 - b. *Griffith Empathy Scale*.⁵⁶ The Griffith Empathy Measure⁰ is a 23-item caregiver rating scale that assesses both affective and cognitive empathy in children and adolescents. The measure was adapted from Bryant's Index of Empathy³² by Dadds and colleagues.
2. Social Cognition Composite (Baseline, Week 12, Week 16, Week 20)
 - a. *Reading Mind in Eyes Test (RMET)*. The RMET examines an individual's ability to determine what a person is thinking or feeling based on photographs of the eye region of male and female faces. A computerized, combined child and adult version of the RMET will be used in the trial reflecting clinical measurements employed in a larger, NIH-funded monotherapy trial of oxytocin vs. placebo⁵⁷.
 - b. *Diagnostic Analysis of Nonverbal Accuracy-2 (DANVA2)*⁵⁸. The DANVA2 examines emotion recognition using both visual and auditory stimuli. Participants were administered all subtests of the DANVA2.

Secondary Outcome Measures. While functional improvements are not expected to be clinically significant within the brief intervention, we will assess changes in social and quality of life metrics as secondary outcomes with the following measures.

1. Global functioning

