Participants entering the study will undergo the baseline assessments, which are anticipated to take approximately 6-10 hours to complete no more than 21 days from the last screening visit. The visit can be split into as many as three visits if this is better for the participant. The following measures will be completed: the CGI-S (Global and Social), AE rating form, the RMET, the CASI-5, the RBS-R, the SRS, the BASC-3, the PDDBI-SV, the Griffith Empathy Scale, the Children's Communication Checklist, the Caregiver Strain, the DANVA2, the TAT, and the Test, GEMEP emotion recognition test, and sensor-based social-communication monitoring tests..

Vineland Scales of Adaptive Functioning (3rd edition): The VABS-3 is a survey administered to a parent or caregiver is organized around four Behavior Domains: Communication, Daily Living Skills, Socialization, and Motor Skills. The VABS-3 will take the parent/caregiver/LAR approximately 20-60 (average 30) minutes to complete, depending on the subject's age and level of functioning.

Weekly Visits (1-11)

Interventions are delivered in 12-session modules occurring on a weekly basis. Groups will commence when all participants in a cycle have completed baseline evaluations and within 21 days of participant's last baseline visit. Participants will receive group treatment conditions as described in Section 5.1 (Treatment Conditions). Participants randomized to ION will also be prescribed 24 IU (3 puffs/nostril) of intranasal oxytocin 4 times/week to be administered by the parent 30-minutes prior to homework practice (3 x/week) and 30 minutes prior to each weekly group session.

Safety ratings during group: Weeks 1, 3, 5, 7, 9, 11 (or biweekly schedule depending on group start day/date)

Vital signs, temperature, and AE ratings will be completed in 6/12 sessions by a licensed physician on participants in all groups. In addition, the CGI-I (Global and Social) will be completed by the Study clinician. At

Confidential

Rush University Medical Center

Week 6, the CY-BOCS, the CASI-5, the RBS-R, the PDDBI-SV, the Griffith Empathy Scale, the Children's Communication Checklist, the Caregiver Strain and the ABC will be completed. In addition, a two week supply of study drug will be dispensed at weeks 1, 3, 5, 7, 9, 11. Unplanned visits will be permitted if there are any concerns about AEs. Safety visits are expected to take 15-20 minutes.

Week 6 (Midpoint)

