| | Scrn (1-2) | Scn/ BL (1-2) | WK1 | WK2 | WK3 | WK4 | WK5 | WK6 | WK7 | WK8 | WK9 | WK10 | WK11 | WK12 | WK16 | Wk24 |
|--|---------------|---------------------|-----|-----|-----|-----|-----|-----|-----|-----|-----|------|------|------|------|------|
| Parent Questionnaires | | | | | | | | | | | | | | | | |
| ABC | X | | | | | | | X | | | | | | X | X | X |
| PDDBI-SV | | X | | | | | | X | | | | | | X | X | X |
| Griffith Empathy Scale | | X | | | | | | X | | | | | | X | X | X |
| Children's Communication Checklist | | X | | | | | | X | | | | | | X | X | X |
| CASI-5 | | X | | | | | | X | | | | | | X | X | X |
| Caregiver Strain | | X | | | | | | X | | | | | | X | X | X |
| Vineland 3 (Survey Form) | | X | | | | | | | | | | | | X | | X |
| SRS-2 | | X | | | | | | X | | | | | | X | X | X |
| RBS-R | | X | | | | | | X | | | | | | X | X | X |
| Autism Impact Measure | | X | | | | | | X | | | | | | X | X | X |
| Parent expectancy questionnaire | | X | | | | | | | | | | | | X | X | X |
| SSIS | | X | | | | | | | | | | | | X | X | X |
| Participant Assessments | | | | | | | | | | | | | | | | |
| Strange Stories Test | X | | | | | | | | | | | | | | | |
| Reading Mind in Eyes Test ¹ | | X | | | | | | | | | | | | X | X | X |
| DANVA2 ¹ | | X | | | | | | | | | | | | X | X | X |
| TAT ¹ | | X | | | | | | | | | | | | X | X | X |
| Biological motion task ¹ | | X | | | | | | | | | | | | X | X | X |
| AEDEA | | X | | | | | | | | | | | | X | X | X |
| Medication | | | | | | | | | | | | | | | | |
| Dosing Instructions | | | X | | X | | X | | X | | X | | X | | | |
| Medication Dispensing Log (staff) | | | X | | X | | X | | X | | X | | X | | | |
| Medication Compliance | | | X | | X | | X | | X | | X | | X | X | X | |
| Medication Diary Dispensed | | | X | X | X | X | X | X | X | X | X | X | X | | | |

Confidential

Rush University Medical Center

WORKS CITED

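### Both social behavior components are collected at Week 6, but the Protocol's primary model leaves that visit out, so some children with on-treatment data can be dropped and the Week 12 effect can be modestly biased

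*Protocol*

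**What the plan says.** Protocol 4.2 defines the first co-primary outcome from two caregiver scales, the Griffith Empathy Scale and the Children's Communication Checklist (CCC), and gives its schedule as "Social Behavior Composite. (Baseline, Week 12, Week 16, Week 20". Week 6 is not listed.

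The visit schedule does include it. Protocol 5.2 says under the weekly visits that at Week 6 "the Griffith Empathy Scale, the Children's Communication Checklist, the Caregiver Strain and the ABC will be completed", and again under Week 6 (Midpoint) that "Griffith Empathy Scale, Children's Communication Checklist, CASI-5, Caregiver Strain, Vineland 3, SRS-2, RBS-R, and AIM will be collected at midpoint". In Appendix A both scales are marked in the WK6 column. None of these places limits the questionnaires to one arm, and the safety ratings at the in-treatment visits are done "by a licensed physician on participants in all groups".

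Protocol 8.8 says that the mixed model will be "conducted on all participants with at least two of four available time points (Wk 0, Wk 12, 1-mon, 3-mo".

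For early leavers, Protocol 5.2 (Termination Visit) asks them to "complete all endpoint study procedures on their final visit before withdrawal to allow for true intent to treat analysis". It does not say which time level that assessment takes in the model.

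The SAP (Data Analysis) gives 12-week change only as an example of the time term, lists no time points, does not repeat the two-of-four rule, and takes the participant as the random effect. Its Data Reduction section forms composites at every time point without naming them.

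**The concern.** A likelihood-based mixed model can allow for dropout that depends on outcomes already observed, but only if those outcomes are in the model. Week 6 is the last scheduled measurement of the social behavior composite before Week 12. If children leave between the two visits because of how they were doing at Week 6, that score is the information the model needs. Protocol 8.8 leaves it out. Its entry rule then goes further and can remove the child altogether, because baseline plus Week 6 counts as one of the four listed points.

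At stake are the Week 12 estimate for one of two co-primary outcomes and the stated aim of an intent-to-treat analysis. Higher composite scores mean more impairment, so a negative effect favors ION-ASD. If ION-ASD children with poor early change leave selectively, the estimate is pushed further in favor of ION-ASD. Selective loss in the control arm, or of children doing well, would push it the other way.

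**Working it through.** **1. Schedule against model**

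| | Wk 0 | Wk 6 | Wk 12 | Wk 16 (1 mo) | Wk 24 (3 mo) |
|---|---|---|---|---|---|
| Griffith, CCC (Appendix A) | yes | yes | yes | yes | yes |
| RMET, DANVA2 (Appendix A) | yes | no | yes | yes | yes |
| Model, Protocol 8.8 | yes | no | yes | yes | yes |
| Model, SAP | not listed | not listed | 12-week change, as an example | not listed | not listed |

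**2. Who fails the two-of-four rule**

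- Wk 0 and Wk 6 only: one of four, excluded.
- Wk 0, Wk 6 and an exit battery: kept or not, depending on how the exit visit is coded.
- Wk 0, Wk 6 and a 1- or 3-month visit: two of four, kept.

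**3. The plan's own figures.** Protocol 8.9 gives 25 per group, 5% attrition, difference 0.40, SD of differences 0.670 and 80% power. As a one-sample or paired test on 24 children, the noncentrality is 0.40/0.67 × √24 = 2.93 and the power is 0.80, so the figure reproduces in that form. A two-arm t-test with 24 per arm gives about 0.53. That is a separate matter. Only 0.40, 0.67 and 5% are used below. At 5%, 2.5 of 50, 3.5 of 70, 4 of 80 or 4.5 of 90 children would be lost.

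**4. Bias by hand.** Let p be the share of an arm lost after Week 6, s the baseline-to-Week 6 change standardized within the arm, m the mean of s among leavers, σ the SD of the Week 12 change, and r the correlation between the Week 6 and Week 12 changes. The mean change of the children who stay is off by

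shift = −[p/(1 − p)] × r × σ × m.

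With a constant correlation ρ between visits, the covariance of the two changes is proportional to 1 − ρ and each variance to 2(1 − ρ), so r = 0.5 for any ρ. Take σ = 0.67. Assume a logistic dropout probability q(s) = 1/(1 + exp(−(a + βs))), with a set so that the mean of q is p. Then m = E[s·q(s)]/p. The slopes β = 1 and β = 2 are assumptions.

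- All of the 5% in ION-ASD (10% against 0%): m = 0.82 or 1.28. The shift is 0.111 × 0.5 × 0.67 × 0.82 = 0.030, or 0.111 × 0.5 × 0.67 × 1.28 = 0.048.
- 5% in each arm, selective in ION-ASD only: m = 0.89 or 1.47. The shift is 0.0526 × 0.5 × 0.67 × m = 0.016 or 0.026. If each visit has SD 1 and ρ = 0.5, then σ = √(2 × 0.5) = 1 and the shift is 0.023 or 0.039.
- Same rate and mechanism in both arms: the shifts cancel and the bias is 0.
- Random loss: m = 0 and the bias is 0.

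**5. Large-sample simulation** (400,000 per arm, true effect −0.40, assumed Week 6 effect −0.20, σ = 0.67, ρ 0.5 to 0.7, slopes 1 to 2, selective loss in both arms; regression on all earlier visits stands in for a mixed model with unrestricted covariance)

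| Loss, ION-ASD / control | Two-of-four, no Week 6 | Baseline-only children kept, no Week 6 | Week 6 added |
|---|---|---|---|
| 5% / 5% | −0.40 | −0.40 | −0.40 |
| 10% / 0% | −0.43 to −0.45 | −0.42 to −0.44 | −0.40 |
| 20% / 5% | −0.44 to −0.46 | −0.42 to −0.44 | −0.40 |
| 30% / 10% | −0.46 to −0.48 | −0.43 to −0.46 | −0.40 |

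The hand formula agrees. For 20%/5% it gives 0.25 × 0.335 × 0.69 − 0.016 = 0.042 at slope 1. The middle column shows that dropping the entry rule alone removes only part of the bias.

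**6. Limit of a random intercept.** If correlations decay over time, with ρ = 0.5 and 15% loss that is selective in ION-ASD only, the random-intercept model gives about −0.52 without Week 6 and about −0.45 with it. The bias is reduced but not removed.

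**7. Scale.** The standard error of the difference is 0.67 × √(2/24) = 0.19 with 24 per arm, or 0.67 × √(2/35) = 0.16 with 35. A bias of 0.05 is 0.26 to 0.31 of that. Under purely random dropout, adding Week 6 lowers the SD of the estimate by only about 1% to 4%.

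**The case against.** The case for leaving the plan alone has weight.

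- A reader might infer that every child lost after Week 6 is excluded. The documents do not say so. Leavers are asked for the full endpoint battery, and a 1- or 3-month visit also satisfies the rule. If half of leavers complete the exit battery, the case of 5% loss with selective dropout in ION-ASD only gives about −0.41 to −0.43. This stands. What remains is that the battery is only requested, and that its time level is undefined.
- A reader might infer that the SAP excludes Week 6. It is silent, and without the two-of-four rule its model need not drop anyone. This also stands, but silence leaves an analyst choice open on a co-primary outcome.
- Outcome-driven dropout is not a documented fact. None of the withdrawal criteria uses a Griffith or CCC score. It is plausible: only ION-ASD children receive the drug, families know their allocation, and caregivers rate the composite. It remains an assumption.
- Large biases need large losses. With dropout selective in ION-ASD only, 15% loss per arm gives about −0.45 to −0.51 and 25% about −0.48 to −0.56, but the only attrition figure in the plan is 5%.
- Omitting Week 6 is coherent. It gives both co-primaries one time structure, and the theory-of-mind module has not been delivered by then. However, Week 6 can inform the Week 12 contrast without becoming an endpoint.

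**Conclusion.** The point holds as a cheap improvement. The Protocol measures both parts of a co-primary composite at Week 6 and then omits that visit from the model. Its entry rule can drop a child who has only baseline and Week 6 values.

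At the planned 5% attrition, the bias in the Week 12 effect is about 0 to 0.05 on the composite's z-score scale, or up to about 12% of 0.40. The upper end requires all loss to fall in one arm and to depend strongly on Week 6 change. Unequal rates are not necessary: equal rates with different reasons for leaving give about 0.02 to 0.04. Loss that is random, or has the same rate and mechanism in both arms, gives none. The correlations, dropout slopes and loss rates above 5% are assumptions.

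Two stronger conclusions are not supported: that the planned analysis is seriously biased, and that adding Week 6 guarantees an unbiased estimate. The second holds only if loss depends on data in the model and the covariance is adequate. The point does not apply to social cognition.

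**What to change.** In Protocol 8.8 and the SAP:

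- Add Week 6 as a categorical time level in the social behavior model (Wk 0, 6, 12, 16, 24), and align the schedule in Protocol 4.2, which names Week 20 where Appendix A has Week 24.
- Replace the entry rule for this composite with at least two of five time points.
- Keep the Week 12 condition-by-time contrast as the estimate.
- Preferably use an unstructured within-child covariance, or report it as a sensitivity analysis to the random intercept. Five time levels mean 5 × 6/2 = 15 covariance parameters, so convergence in a small trial should be planned for.
- State which time level an early-termination assessment receives.
- Leave social cognition on four time points, because RMET and DANVA2 are not scheduled at Week 6.

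The cost is a few sentences and no new assessments. The SAP already standardizes on baseline mean and SD, so Week 6 scores go onto the same scale unchanged. The downsides are different time levels in the two co-primary models and little gain in precision if dropout is random.
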